1.0 PROTOCOL SUMMARY AND/OR SCHEMA

For this proposed Phase III study, intermediate risk prostate cancer patients will be randomized to receive 6 months of Androgen Deprivation Therapy (ADT) in conjunction with stereotactic body radiosurgery (SBRT) directed to the prostate versus SBRT alone. The patient population eligible will include patients with NCCN defined intermediate risk disease. ADT will be administered with Degarelix monthly injections. SBRT will be delivered with a prescription dose of 8 Gy x 5 to the planning target volume. Inter-fraction motion targeting and target position corrections will be utilized for each of the 5 treatment fractions. All patients will be followed every 6 months for 2 years and will undergo routine 24-30 months post-SBRT prostate biopsies to assess for local tumor control.

2.0 OBJECTIVES AND SCIENTIFIC AIMS

Primary Objectives

- To compare 24-30 month post-SBRT prostate 12 core biopsy outcomes between intermediate risk patients treated with SBRT and short course ADT versus SBRT alone.

Secondary Objectives

- To assess whether the addition of 6 months of ADT with high dose SBRT decreases incident rates of biochemical failure and distant failure, or improves survival rate for intermediate risk prostate cancer patients compared to SBRT alone.
- To assess the differences in short-term and long-term quality of life outcomes by comparing EPIC-26, IPSS, and SF-12 survey results between intermediate risk prostate cancer patients treated with SBRT + short course ADT versus SBRT alone.

3.0 BACKGROUND AND RATIONALE

3.1 Improved Outcomes with ADT and Conventionally Fractionated EBRT for Intermediate Risk Disease

Data from two randomized trials have demonstrated survival advantages when using short course ADT in conjunction with low dose (70 Gy) conventionally fractionated radiotherapy for patients with intermediate risk disease (1, 2). While these studies have not confirmed the need for ADT in the era of dose escalation in the ranges of 78-80 Gy it is assumed that ADT would be advantageous as well even when higher radiation dose levels are employed.

Retrospective data from Memorial Sloan-Kettering Cancer Center have demonstrated that improved distant metastases-free survival and prostate cancer mortality survival outcomes are observed with the addition of short course ADT to high-dose (≥ 81 Gy) conventionally fractionated radiotherapy among patients with intermediate risk disease (3). Between 1992 and 2007, 1024 patients with NCCN intermediate risk prostate cancer were treated at Memorial Sloan Kettering Cancer Center and its regional facilities with definitive external beam radiation with doses of ≥ 81 Gy. Unfavorable intermediate risk factors were defined as primary Gleason score (GS) of 4, percentage of positive biopsy cores (PPBC) $\geq 50\%$, and more than one intermediate risk factors (IRF). Unfavorable intermediate risk patients had at least one of these factors, whereas favorable intermediate risk patients had none, with a median follow-up was 6 years. 51% of patients received short-course androgen deprivation therapy (ADT). In that study we noted that ADT was associated with an improvement in all outcomes in our multivariate models. Patients with unfavorable intermediate risk disease had inferior rates of PSA-RFS (HR = 2.37, 95% CI: 1.68-3.36, P <0.0001), DM (HR=4.34, 95% CI: 1.95-9.67, P=0.0003), and PCSM (HR=7.39, 95% CI: 1.75-31.31, P = 0.007) compared to those with favorable intermediate risk disease. Patients with multiple unfavorable risk factors had particularly poor prognosis, with 8 year rates of PSA-RFS, DM, and PCSM of 60%, 23%, and 12%, respectively. Benefits of using ADT were most noted among patients with intermediate risk features with unfavorable characteristics. In a prior publication we also noted improved post-treatment biopsy outcomes among patients who were treated with external beam radiotherapy (EBRT) with the addition of a short-course of ADT compared to external radiotherapy alone short course NAAD had a significant impact on the posttreatment biopsy outcome. Of patients who did not receive ADT 86 of 206 (42%) had a positive biopsy compared to 21 of 133 (16%) who received ADT (p <0.0001). Zelefsky MJ, Reuter VE, Fuks

Z, et al. Influence of local tumor control on distant metastases and cancer related mortality after external beam radiotherapy for prostate cancer. J Urol. 2008 Apr;179(4):1368-73. In a recent update among intermediate risk patients who underwent post-treatment biopsies the incidence of a positive biopsy among those who received short course ADT with EBRT was 15% compared to 35% among those treated with EBRT alone (p< 0.001)[unpublished data]

3.2 Clinical Outcomes with SBRT for Prostate Cancer

Stereotactic hypofractionated radiotherapy is commonly utilized as a form of definitive therapy for patients with favorable and intermediate risk prostate cancer. There have been multiple retrospective studies indicating excellent PSA relapse-free survival outcomes at 5 years and low rates (<2%) of grade 3 or higher urinary or rectal toxicities (4-9). In 2009 we initiated a Phase I-II dose escalation study where favorable and intermediate risk prostate cancer patients were treated with SBRT to the prostate. The initial dose level was 32.5 Gy in 5 fractions. After 30 patients were accrued the next dose level was initiated at 35 Gy in 5 fractions for the subsequent 30 patients. Escalation of dose continued in this fashion to 37.5 Gy in 5 fractions and finally 40 Gy in 5 fractions. Accrual to the study completed 6 months ago and to date no grade 4 toxicities have been observed at any of the dose levels and the incidence of grade 3 rectal or urinary toxicities has been < 2%. The current prescription dose used at MSKCC for SBRT is 40 Gy in 5 fractions and the excellent tolerance associated with treatment can be attributed to several factors including: the use of tight margins of 5 mm around the circumference of the clinical target volume and 3 mm at its posterior aspect, and the use of image guidance with inter-fraction and intra-fraction motion correction for enhanced accuracy. Because of the short duration of therapy compared to conventionally fractionated IMRT which spans for 10 weeks, SBRT to 40 Gy in 5 fractions has become the most common mode of external beam radiotherapy at Memorial Sloan Kettering Cancer Center. While the median follow up in this experience is 24 months, the PSA relapse rates have been <15% at 3 years. Currently RTOG 0938 is in the midst of a randomized Phase II trial which compares 36.25 Gy in 5 fractions using 7.25 Gy compared to 51.6 Gy in 12 fractions of 4.3 Gy. In the study the eligibility criteria include favorable risk patients and the primary endpoint in that study is 12 month health related quality of life outcomes for treated patients.

3.3 Study Rationale

To date there have been no studies exploring the impact of short course ADT for intermediate risk patients who are treated with SBRT. On the one hand the use of high dose SBRT with its greater radiobiological dose delivery may obviate the need for short course ADT and potentially reduce the deleterious impact this therapy would have on the quality of life of the individual patient. On the other hand, the addition of short course ADT even in the setting of high dose SBRT may further improve survival outcomes especially among the cohort of intermediate risk patients with more unfavorable disease characteristics as has been demonstrated in published Phase III trials when conventionally fractionated radiotherapy was used (1, 2). With the increasing number of patients being treated with SBRT at our institution and in the United States, this issue is of significant clinical importance. This study will evaluate the tumor control outcomes in each group and as the primary objective of this study we will evaluate local tumor control with a 2- year post treatment biopsy considered to represent an excellent surrogate endpoint for local disease control and more reflective of this endpoint than PSA-relapse-free survival. This biopsy endpoint has been successfully used in our Phase I dose escalation study (IRB- 09-035) evaluating local control in SBRT treatment patients. However, in addition to 2 year biopsy outcomes, biochemical control and distant metastases-free survival will also be evaluated.

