4.0 OVERVIEW OF STUDY DESIGN/INTERVENTION

4.1 Design

For this proposed Phase III study, intermediate risk patients will be randomized to received 6 months of ADT which would be given 3 months prior to planned SBRT to the prostate and 3 months during/following SBRT. ADT will be administered via Degarelix monthly injections. SBRT will be delivered with a prescription dose of 8 Gy x 5 prescribed to the planning target volume. Inter-fraction motion targeting and target position correction will be utilized as is routine in our department during the treatment SBRT.

The primary end-point of this study is the proportion of patients who have positive 2-year post-treatment prostate biopsies. Based on our previous published experience, we expect that the 2-year rate of a positive biopsy using ADT with ultra-hypofractionated SBRT for intermediate risk features would be 15% compared to 35% for those patients treated with SBRT alone. We anticipate we would require powering the study with 100 patients in each arm. Randomization will be stratified by favorable-intermediate and unfavorable-intermediate risk status (unfavorable-intermediate risk will be defined as patients having Gleason 4+3, >50% positive biopsy cores or 2 intermediate risk factors combined such as Gleason 7 and PSA > 10 ng/ml).

The primary endpoint is the 2-year biopsy which is generally scheduled at the end of the second year. However, we have provided some flexibility as to prevent prospective and retrospective deviations. Therefore, we have chosen to allow the primary endpoint biopsy to occur between 24-30 months which we believe is reasonable based on our clinical experience.

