14.0 BIOSTATISTICS

The primary objective of this phase III trial is to compare 2-year biopsy positivity rate of intermediate risk prostate cancer patients treated with SBRT + short course ADT versus SBRT alone. The 2-year biopsy positivity rate will be calculated in each arm as a proportion of patients whose 2-year (from the end of SBRT) biopsy result is positive over patients who have 2-year biopsy results examined or whose 2-year biopsy results are regarded as positive (see the replacement rule below). We plan to analyze an evaluable sample of 200 patients, randomized in a 1:1 ratio to the two arms. This sample size has a power greater than 0.90 and type 1 error rate of 0.05 if the true 2-year biopsy positivity rates are 35% and 15% respectively, for the two arms using a two-sided, two-sample proportion test. This test will also be adjusted for the randomization stratification variables. Patients who died due to disease within 2 years from the end of SBRT will be regarded as having a positive biopsy. Patients who died not due to disease or are lost to follow-up within 2 years from the end of SBRT without any sign of progression will be replaced. To this end we will enroll an additional 10% patients upfront so the total sample size is 223. However, only the first 200 evaluable patients will be counted towards the primary endpoint. One interim analyses and one final analysis are planned (using equal spacing of looks) and the null hypothesis that the two arms have the same 2-year biopsy positivity rates will be rejected at these two looks if the p-values are <0.003 and <0.049, respectively, based on the Lan-DeMets alpha spending function approach. We expect that 100 patients will be enrolled each year, 50 from MSK and 50 between all regional sites. Therefore we anticipate to complete the enrollment in 2-3 years, plus an additional 2-year mandatory follow-up.

For the secondary objectives, the cumulative incidence rates of biochemical failure and distant failure will be evaluated by the competing risks method and Gray's test will be used to compare the two arms. Overall survival rates will be estimated by Kaplan-Meier method and compared by log-rank tests. QOL outcomes will be summarized and tabulated. Results from the two arms will be compared by Wilcoxon rank sum tests at time points when these surveys are conducted. All patients will be analyzed for the secondary objectives.

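### Randomization is stratified by favorable vs unfavorable intermediate risk, but Section 14 uses that factor only to adjust the pooled primary test: the Gray and log-rank tests are described without it, and no arm difference by stratum is pre-specified.

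*Combined protocol and SAP*

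**What the plan says.** - **Background (Section 3.1).** In the institution's retrospective series of 1,024 intermediate-risk patients, those with unfavorable features did worse than favorable patients: HR 2.37 for PSA relapse-free survival, 4.34 for distant metastases and 7.39 for prostate cancer mortality. On ADT it reports: "Benefits of using ADT were most noted among patients with intermediate risk features with unfavorable characteristics".
- **Rationale (Section 3.3).** High-dose SBRT may make short-course ADT unnecessary in intermediate-risk patients. Alternatively, ADT "may further improve survival outcomes especially among the cohort of intermediate risk patients with more unfavorable disease characteristics".
- **Randomization (Sections 4.1 and 15.2).** Permuted blocks, stratified by favorable vs unfavorable intermediate risk.
- **Primary analysis (Section 14.0).** A pooled comparison of biopsy positivity in 200 evaluable patients, 35% vs 15%, "using a two-sided, two-sample proportion test". On the stratum, Section 14 says only: "This test will also be adjusted for the randomization stratification variables".
- **Secondary analyses (Section 14.0).** Gray's test for biochemical and distant failure and log-rank for survival, each comparing the two arms with no mention of the stratum. No by-stratum estimate, interaction or subgroup analysis is planned.
- **Stratum definition.** Section 3.1 counts at least 50% positive cores as unfavorable. Section 4.1 uses ">50% positive biopsy cores or 2 intermediate risk factors combined", alongside Gleason 4+3. The difference is not explained.

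**The concern.** The factor matters for two separate reasons.

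First, it is reported as strongly prognostic for the kinds of event that the secondary tests compare. If patients are randomized within a strong prognostic factor and the time-to-event test then ignores it, precision that the design already provides is lost. The primary test avoids this; the secondary tests, as described, do not.

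Second, it is the one factor that the background singles out as marking where ADT benefit was most seen. Readers will want the biopsy result split this way. If the split is not pre-specified, any later version is post hoc, and its definition, scale and status are open to choice after the data are known. A pooled positive result would not by itself show how the effect is shared between strata. A pooled null could coexist with a real effect in one of them.

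**Working it through.** **Inputs from Section 14.** 100 evaluable patients per arm; rates 35% and 15%; two-sided "type 1 error rate of 0.05"; final-look level 0.049. "This sample size has a power greater than 0.90", the plan states. The documents give neither the unfavorable share nor any stratum-specific biopsy rate, so every by-stratum figure below rests on assumed values.

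**1. The plan's own power.** Power = Φ{(|p1 − p2| − 1.96·√[2p̄(1 − p̄)/n]) / √[(p1(1 − p1) + p2(1 − p2))/n]}.

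With n = 100 and p̄ = 0.25, the null SE is 0.0612 and the alternative SE 0.0596. Then (0.20 − 1.96 × 0.0612)/0.0596 = 1.34, and Φ(1.34) = 0.91. At level 0.049 it is 0.909. The stated figure reproduces.

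**2. Precision within a stratum.** Half-width = 1.96·√[(0.35 × 0.65 + 0.15 × 0.85)/m] = 1.96·√(0.355/m), with m patients per arm in the stratum. The last column uses the power formula of step 1.

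| m per arm | 95% CI half-width | Interval around 20 points | Power at 35% vs 15% |
|---|---|---|---|
| 30 | 21.3 points | −1.3 to 41.3 | 0.43 |
| 50 | 16.5 points | 3.5 to 36.5 | 0.64 |
| 70 | 14.0 points | 6.0 to 34.0 | 0.79 |
| 100 (pooled) | 11.7 points | 8.3 to 31.7 | 0.91 |

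**3. Interaction.** Assume 35% vs 15% in unfavorable patients and 35% vs 35% in favorable patients, 50 per arm in each stratum.

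- Difference scale: SE = √(0.355/50 + 2 × 0.2275/50) = 0.127; z = 0.20/0.127 = 1.57; power 0.35. The half-width is 1.96 × 0.127, about 25 points.
- Log-odds scale: the contrast is ln(0.35/0.65) − ln(0.15/0.85) = 1.116; SE = √[(1/0.2275 + 1/0.1275)/50 + 2/(0.2275 × 50)] = 0.649; z = 1.72; power 0.41.

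| Unfavorable share | Power, difference scale | Power, log-odds scale |
|---|---|---|
| 30% | 0.31 | 0.33 |
| 50% | 0.35 | 0.41 |
| 70% | 0.29 | 0.37 |
| 80% | 0.23 | 0.31 |

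A sharper assumed contrast (45% vs 15% unfavorable, 20% vs 20% favorable) gives 0.41 to 0.72 over the same shares.

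**4. Illustration of what a pooled contrast can conceal.** Assume a 50:50 mix, 35% control positivity in both strata and no effect in favorable patients. The pooled ADT rate is 0.5 × 15% + 0.5 × 35% = 25%. With p̄ = 0.30, (0.10 − 1.96 × 0.0648)/0.0644 = −0.42, so power is 0.34. At a 30% unfavorable share it is 0.15, and at 70% it is 0.60. These figures describe an assumed extreme, not the trial's expected power.

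**5. Cut-point.** The two definitions differ only for a patient with exactly 50% positive cores and no other unfavorable feature. The documents do not say how many such patients to expect.

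**The case against.** The strongest reply is that the trial answers the question it asks. Section 2.0 compares the arms in intermediate-risk patients and has no objective about which stratum benefits. Eligibility matches that objective, randomization is stratified, and the primary test is adjusted. The biopsy evidence behind the design (35% vs 15%) is pooled, and no document reports a biopsy effect that differs by stratum. By-stratum results would often be inconclusive. All of this stands, and it makes this an improvement to the analysis plan rather than a design failure.

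It also rules out several stronger readings:

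- *The trial cannot say who benefits.* The stratum is recorded at randomization, so effects within strata can be estimated. They are simply not pre-specified.
- *The rationale suspects that favorable patients in particular need no ADT.* The remark in Section 3.3 that SBRT may make ADT unnecessary covers intermediate-risk patients generally. Its comment on unfavorable patients is hedged and concerns survival, not biopsy.
- *The cut-point difference causes the gap, or patients are misplaced by it.* Section 4.1 does not claim to adopt the Section 3.1 definition, and the number affected is unknown. Nor can it be illustrated from a 12-core biopsy: the documents specify 12 cores for the post-SBRT biopsy, not for diagnosis.

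The reply does not remove the core point. The stratum is prognostic, is already collected and balanced, and is left out of the secondary tests and of any planned presentation of the primary result.

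**Conclusion.** The point holds as a gap in Section 14, at modest severity. The randomization factor adjusts the primary test and is used nowhere else, although the background reports it as strongly prognostic and as marking where ADT benefit was most seen.

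The sample size is adequate for the pooled question. A reader might infer from the 0.34 in the illustration that the trial is underpowered. The documents do not support that, because the figure needs an assumed mix, assumed equal control rates and an assumed zero effect in one stratum.

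The precision lost by leaving the Gray and log-rank tests unstratified cannot be sized from the documents, which give no event rates by stratum in this setting; the hazard ratios come from conventionally fractionated treatment. By-stratum biopsy estimates are worth having but would be supportive only, because their intervals are wide and interaction power is low under the assumed scenarios. The cut-point difference is a separate, minor inconsistency.

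**What to change.** In Section 14:

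1. Stratify the Gray and log-rank comparisons by the randomization factor.
2. Pre-specify the arm difference in biopsy positivity with a 95% CI within the favorable and unfavorable strata, plus an arm-by-stratum interaction estimate, naming its scale.
3. Label item 2 supportive and state the expected precision from the working above, so that a non-significant interaction is not read as evidence of a uniform effect.

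In Sections 3.1 and 4.1, reconcile the positive-core cut-point or explain why it differs. Whichever is chosen, keep the stratum as randomized for the adjusted and stratified tests, and state which definition the by-stratum estimates use.

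The cost is SAP wording and one additional table, with no change to sample size, eligibility or the primary test. Explaining the cut-point takes a sentence. Changing it would need a protocol amendment and an update to the randomization system, and during accrual would mix two definitions, so an explanation may be the better course.

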4.0 OVERVIEW OF STUDY DESIGN/INTERVENTION

4.1 Design

For this proposed Phase III study, intermediate risk patients will be randomized to received 6 months of ADT which would be given 3 months prior to planned SBRT to the prostate and 3 months during/following SBRT. ADT will be administered via Degarelix monthly injections. SBRT will be delivered with a prescription dose of 8 Gy x 5 prescribed to the planning target volume. Inter-fraction motion targeting and target position correction will be utilized as is routine in our department during the treatment SBRT.

The primary end-point of this study is the proportion of patients who have positive 2-year post-treatment prostate biopsies. Based on our previous published experience, we expect that the 2-year rate of a positive biopsy using ADT with ultra-hypofractionated SBRT for intermediate risk features would be 15% compared to 35% for those patients treated with SBRT alone. We anticipate we would require powering the study with 100 patients in each arm. Randomization will be stratified by favorable-intermediate and unfavorable-intermediate risk status (unfavorable-intermediate risk will be defined as patients having Gleason 4+3, >50% positive biopsy cores or 2 intermediate risk factors combined such as Gleason 7 and PSA > 10 ng/ml).

The primary endpoint is the 2-year biopsy which is generally scheduled at the end of the second year. However, we have provided some flexibility as to prevent prospective and retrospective deviations. Therefore, we have chosen to allow the primary endpoint biopsy to occur between 24-30 months which we believe is reasonable based on our clinical experience.

4.2 Intervention

Eligible patients with intermediate risk disease will be randomized to ADT with SBRT versus SBRT alone. The ADT patients will be treated with monthly degarelix injections. After three months (+/- 1 month) have elapsed, these patients as per routine would undergo fiducial marker placement followed by simulation and SBRT to follow. For this cohort ADT will continue until 6 months of Degarelix is administered. If a patient develops an allergic reaction to the Degarelix injection, he may be switched to Leuprolide acetate monthly injections in its place.

For patients treated with SBRT alone referral will be made for fiducial marker placement with simulation and SBRT to follow. Patients will then be followed at 6 month intervals with routine serum PSA and testosterone testing. All patients will undergo a post-SBRT standard 12 core prostate biopsy at 24-30 months after completion of SBRT to evaluate local tumor control status.

